1.7. Blinding and Randomization Methods

1.7.1. Blinding Method

Treatment Arms A and B

This is a double-blind study. The blinding method is described in protocol section 5.1 Randomization and Blinding.

Open-Label Substudy Treatment Arm C

The substudy is open-label.

1.7.2. Randomization Method

For Treatment Arms A and B, central randomization was implemented in this study. The randomization scheme was implemented within the Interactive Web Response System (IWRS).

Randomization was stratified using the following stratification factors and subjects were randomized in a 1:1 ratio to receive either ibrutinib + rituximab or placebo + rituximab within each randomization stratum:

a) WM International Prognostic Scoring System (IPSS) assessed at screening (low vs. intermediate vs. high)

- b) Number of prior systemic treatment regimens (0 vs. 1-2 vs. \geq 3)
- c) Eastern Cooperative Oncology Group [ECOG] (0-1 vs. 2)

1.8. Independent Data Monitoring Committee

The safety and the interim analysis of this study are monitored by an independent data monitoring committee (DMC). The independent DMC may recommend stopping the study for efficacy if the pre-specified stopping boundary is crossed at the interim analysis. In addition to the ongoing safety monitoring and planned interim analyses for efficacy, periodic safety review meetings are planned. The plan for monitoring subject safety and evaluating efficacy, and the roles and responsibilities of the independent DMC, are detailed in the independent DMC Charter.

2. GENERAL ANALYSIS CONSIDERATION

Time to event or duration of event endpoints will be based on the actual event date (or censoring date) rather than visit number or visit label. Missing efficacy or safety data will not be imputed unless otherwise specified.

In general, the baseline value is defined as the last valid measurement on or prior to the first dose of study treatment (ibrutinib/placebo, rituximab). For by-visit analysis, visit windows will be used to associate assessment with a scheduled visit and will be created in reference to the date of first dose of study treatment to assign visit number based on assessment date.

2.1. Analysis Sets

Intent-to-Treat Population

The intent-to-treat (ITT) population includes all randomized subjects (Arms A and B), regardless of the actual treatment received. This population will be the primary population for the summary/analyses of efficacy endpoints, disposition, demographics and baseline characteristics and PRO data.

Safety Population

Safety population includes all subjects who received at least 1 dose of study treatment (rituximab, ibrutinib/placebo). Subjects in this population will be analyzed as randomized for the randomized subjects. The safety population will be used to summarize the safety (including dosing) data.

For the open-label substudy (Arm C), disposition, demographics and baseline characteristics, efficacy, PRO and safety outcome will be summarized descriptively based on the safety population.

2.2. Definition of Subgroups

Subgroup analyses will be performed for the selected variables to assess the internal consistency of the treatment benefit and/or safety. The subgroup variables and the cutoff values are subject to change if warranted to better represent the data.

Subgroup	Definition of Subgroup	Analysis Type
Age	<65,≥65	D, E, S
Sex	Male, Female	D, E, S
Prior treatment history as recorded on CRFs	Previously untreated, Previously	D, E, S
	treated	
Race	White, Non-White	Е
Geographic region	US, Non-US	Е
Baseline ECOG as recorded on CRFs	0-1, 2	Е
Baseline IgM	$<40, \ge 40 \text{ g/L}$	Е
Baseline hemoglobin (Hgb)	$\leq 11, > 11 \text{ g/dL}$	Е
Baseline β2-microglobulin	\leq 3, >3 mg/L	Е
WM IPSS as recorded on CRFs	Low, Intermediate, High	Е
MYD88 L265P mutational status	Mutated, No mutation	Е

Table 1: Subgroup Definition

PCYC-1127-CA Statistical Analysis Plan

Subgroup	Definition of Subgroup	Analysis Type
Concomitant use of moderate and/or strong CYP3A inhibitor	Yes, No	S
Baseline creatinine clearance	<60, ≥60 mL/min	S
Baseline liver function based on NCI criteria	Normal, Abnormal (Mild, Moderate, Severe)	S

analysis type D= demographic and baseline disease characteristics

analysis type E= efficacy (Treatment Arms A and B); Considering small sample size in one or more strata, results for race, geographic region, ECOG, MYD88 L265P mutational status may be presented separately.

analysis type S= safety (adverse events)

IWRS= Interactive Web Response System; ECOG= Eastern Cooperative Oncology Group

2.3. Handling of Missing Data for PRO Analysis

Missing Items within Domains

FACT-An scores are derived per FACT-An Scoring Guidelines (Version 4). Fatigue subscale score is derived per FACIT-Fatigue Subscale Scoring Guidelines (Version 4) from the 13 fatigue related items of FACT-An. Similarly, fatigue experience score is calculated from the 5 items (HI7, HI12, An1, An2, An5) assessing fatigue symptoms and fatigue impact score is calculated from the 8 items (An3-An4, An7-An8, An12, An14-An16) assessing the impact of fatigue.

If there are missing items, subscale scores are prorated. This is done by multiplying the sum of the item scores by the number of items in the subscale, then dividing by the number of items answered. A subscale score is calculated only if >50% of the items were answered. The total score is calculated as the sum of the prorated subscale scores. Total scores are calculated only if the overall item response rate is >80% (i.e. at least 22 of 27 items answered for FACT-G total score, and at least 38 of 47 items answered for FACT-An total score).

3. SUBJECT INFORMATION

3.1. Subject Disposition

Subject disposition will be summarized by treatment arm. Subject enrollment will be summarized by region, country, and investigator.

Time on study is defined in the same way as overall survival with reversed censoring, i.e., subjects who died will be censored at death date. The Kaplan-Meier method will be used to estimate the median time on study.

3.2. Demographics and Baseline Characteristics

Baseline characteristics and demographic information at baseline will be summarized with descriptive statistics by treatment arm.

3.3. Prior and Concomitant Medications

Medications will be coded to a generic name and an Anatomical Therapeutic Chemical (ATC) class per the World Health Organization (WHO) drug dictionary. Concomitant medications will be summarized by therapeutic class and preferred term and by treatment arm. Concomitant medications are defined as medications that were taken at any time on treatment (i.e. from the date of the first dose of study treatment through the date of the last dose of study treatment). The following concomitant medications will be summarized separately: growth factors, blood supportive products and immunoglobulin, CYP3A inhibitors/inducers, anticoagulants and/or antiplatelets.

3.4. Extent of Exposure to Study Treatment

Exposure to study treatment will be summarized by treatment arm. Descriptive statistics will be provided for treatment duration and dosing information (e.g. total cumulative dose administered, relative dose intensity, dose reduction due to adverse events) for all study treatments.

3.5. Previous Treatment History and Subsequent Antineoplastic Therapies

Previous treatment history and subsequent WM antineoplastic agents will be summarized separately.

4. EFFICACY AND SAFETY ANALYSES

4.1. Efficacy Analyses

Treatment Arms A and B

Efficacy endpoints and analysis methods for the randomized treatment arms (Arms A and B) are summarized in Table 2.

The following two randomization stratification factors will be used for the stratified analysis/test: WM IPSS assessed at screening (low, intermediate, high) and number of prior systemic treatment regimens $(0, \ge 1)$. Due to limited number of subjects with ≥ 3 prior systemic treatment regimens, subjects with 1-2 or ≥ 3 prior systemic treatment regimens will be categorized into one subgroup (i.e. ≥ 1). All the stratified tests will be based on the randomization stratification factors as recorded in IWRS.

Open-Label Substudy Treatment Arm C

For the open-label Arm C, the efficacy outcome will be analyzed separately from the randomized treatment arms. Time to event variables (e.g. PFS, TTnT, OS, DOR) will be analyzed using Kaplan-Meier estimate. For categorical variables (e.g. ORR, rate of sustained hemoglobin improvement, CRR), 95% confidence intervals (CIs) will be calculated based on the exact binomial distribution. For continuous variables (e.g. IgM, lymph node and spleen measures, tumor involvement of bone marrow), descriptive statistics will be calculated. No comparator analysis will be done with Arms A or B.

Note that date of randomization is not applicable for Arm C subjects, therefore date of the first dose of ibrutinib will be used in calculating efficacy variables.

Table 2: Summary of Efficacy Analyses to be Performed for Arms A and B

Endpoint	Definition	Analysis Methods			
Primary Endpoint					
PFS assessed by IRC	Time from the date of randomization to the date of first IRC-confirmed disease progression (PD) or date of death due to any cause, whichever occurs first, regardless of the use of subsequent antineoplastic therapy prior to documented PD or death. For subjects who do not have IRC-confirmed PD and not known death as of clinical data cutoff, PFS is censored at the date of the last evidence of no progression by IRC.	 The treatment effect of ibrutinib + rituximab (Arm A) compared to placebo + rituximab (Arm B) will be tested with a stratified log rank test adjusted for 2 randomization stratification factors. The hazard ratio and its 95% confidence interval (CI) based on a Cox regression model stratified by the 2 randomization stratification factors will be calculated. Kaplan-Meier analysis for PFS distribution; median PFS estimated with 2-sided 95% CI. Sensitivity Analyses: Subjects who received subsequent antineoplastic therapy are censored at the last disease assessment showing no evidence of PD before the use of subsequent therapy: same analyses as above. Subjects who missed ≥2 consecutively planned disease assessments immediately before IRC-confirmed PD or death are censored at the last disease assessment prior to documented PD or death: same analyses as above. Investigator assessed PFS: same analyses as above. IRC-assessed PFS by unstratified log-rank test and unstratified Cox regression model. 			
Secondary Endpoints					
ORR assessed by IRC	Proportion of subjects achieving a best overall response of confirmed complete response (CR), very good partial response (VGPR), or PR per the IRC assessment at or prior to initiation of subsequent antineoplastic therapy.	ORR will be compared between the two randomized treatment arms (ibrutinib + rituximab vs. placebo + rituximab) using Cochran-Mantel-Haenszel (CMH) chi- square test, adjusted for the 2 randomization stratification factors. 95% CI for the rate ratio will be calculated. Sensitivity Analyses: Investigator assessed ORR: same analyses as above. Subgroup Analyses: Rate ratio and its 95% CI for each subgroup of selected variables (e.g. prior treatment history, MYD88 L265P mutational status).			
Time to next treatment	Time from the date of randomization to the start date of any subsequent WM treatment.	Same as PFS: stratified log-rank test, stratified Cox regression model, and Kaplan-Meier analysis.			

PCYC-1127-CA Statistical Analysis Plan

Endpoint	Definition	Analysis Methods	
(TTnT)	Subjects without subsequent treatment are censored at the date of the last study visit.		
Rate of sustained hemoglobin improvement	Proportion of subjects achieving a sustained improvement in hemoglobin (Hgb) at or prior to initiation of subsequent antineoplastic therapy. Hgb improvement is defined as an increase of ≥ 2 g/dL over baseline regardless of baseline value, or an increase to >11 g/dL with a ≥ 0.5 g/dL improvement if baseline is ≤ 11 g/dL. Sustained Hgb improvement is defined as improvement that is sustained continuously for ≥ 56 days (8 weeks) without blood transfusion or growth factors.	The two randomized treatment arms will be compared (ibrutinib + rituximab vs. placebo + rituximab) using chi- square test. 95% CI for the rate ratio will be calculated. Subgroup Analysis: Chi-square test for subjects with Hgb ≤ 11 g/dL at baseline.	
Proportion of subjects with ≥ 3 points increase from baseline by Week 25 in fatigue experience score	Proportion of subjects with $a \ge 3$ points increase from baseline in fatigue experience score at any time point at or prior to initiation of subsequent antineoplastic therapy by Week 25. Fatigue experience score is calculated from the FACT-An 5 items (HI7, HI12, An1, An2, An5) assessing fatigue symptoms.	The two randomized treatment arms will be compared (ibrutinib + rituximab vs. placebo + rituximab) using chi- square test. 95% CI for the rate ratio will be calculated.	
Overall survival (OS)	Time from the date of randomization to the date of death from any cause. For subjects who were not known to have died at or prior to the clinical cutoff date, OS is censored on the date last known alive.	Unstratified log-rank test, unstratified Cox regression model, and Kaplan-Meier analysis. Exploratory analysis adjusting the crossover effect may be performed, if needed.	
Exploratory E	ndpoints		
Time to sustained hemoglobin improvement	Time from the date of randomization to the initial date of sustained hemoglobin improvement.	Descriptive summary statistics for subjects who achieved sustained hemoglobin improvement.	
DOR by IRC, DOR by investigator	Time from the date of initial documentation of a response (PR or better) to the date of first documented evidence of PD or death for responders (PR or better). The same censoring rules for PFS are used for DOR.	Kaplan-Meier analysis	
CRR by IRC, CRR by investigator	Proportion of subjects achieving a best overall response of confirmed CR, VGPR, PR or MR at or prior to initiation of subsequent antineoplastic therapy.	Same analyses as for ORR	

PCYC-1127-CA Statistical Analysis Plan

Page 16 of 18

Endpoint	Definition	Analysis Methods	
IgM, Hgb	Value and change from baseline	Descriptive summary statistics	
Lymph nodes and spleen	Sum of product of diameters for target nodal lesions, spleen depth and spleen volume	Descriptive summary statistics	
Tumor involvement of bone marrow	Cellularity and intertrabecular space	Descriptive summary statistics	
Medical resource utilization	Number of plasmapheresis, number of emergency room visits, number and days of hospitalizations	Descriptive summary statistics	
EQ-5D-5L visual analog scale and utility score, FACT-An total score and subscale scores	Value and change from baseline, proportion of subjects achieving clinically meaningful improvement, time to improvement. Clinically meaningful improvement is defined as an increase of \geq 7 points for visual analog scale (or \geq 0.08 points for utility score, \geq 7 points for FACT-An total score, \geq 6 points for anemia subscale score, \geq 3 points for fatigue subscale score) prior to initiation of subsequent antineoplastic therapy.	Descriptive summary statistics. The proportion of subjects achieving clinically meaningful improvement will be compared between the two randomized treatment arms using chi-square test. 95% CI for the rate ratio will be calculated. For each parameter, change from baseline up to Week 49 will be analyzed using the Mixed-Effects Model Repeated Measure (MMRM). The model includes the baseline scores, baseline ECOG (0, 1-2), prior treatment history on CRF (previously untreated, previously treated), WM IPSS on CRF (low, intermediate, high) as covariates; treatment, time point and treatment-by-time point interaction as fixed effects; and subjects as random effect. An unstructured (co)variance structure will be used to model the within-subject error. Kenward-Roger's approximation will be used to estimate denominator degrees of freedom. The 2-sided 95% CIs will be calculated	

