Statistical Methods and Data Analysis:	
Primary Efficacy Analysis:
 
The primary efficacy analysis of the randomized study will be performed using the intent-to-treat (ITT) population based on IRC assessed PFS. All subjects will be followed for PFS until a PFS event occurs (progression or death) or until the data cutoff. PFS will be assessed based on the modified VIth IWWM (NCCN 2014) response criteria for WM and will be analyzed using the Kaplan-Meier method. The randomized treatment arms (Arm A and Arm B) will be compared using log-rank test. Subgroup analyses will be performed for selected subgroups (eg, prior WM treatment history: untreated versus previously treated) to assess the consistency of treatment effect across subgroups.
 
Secondary Efficacy Analysis:
 
Multiplicity adjustment for the randomized treatment arm comparisons will be made to control the overall type 1 error based on hierarchical testing procedure. The order of the secondary endpoints will be specified in the Statistical Analysis Plan (SAP). Overall response rate (ORR) will be compared using the chi-square test. The percentage of subjects with sustained hematological improvement as measured by change in hemoglobin level will be presented and compared using the chi-square test. The distribution of the time to improvement will be summarized using the Kaplan-Meier method as appropriate. The distribution of OS and TTnT will be estimated using the Kaplan-Meier method similar to PFS. Survival rate for OS at landmark points will be summarized based on the Kaplan-Meier method.

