10.5. Sample Size Determination (Treatment Arms A and B)

This study is designed to evaluate the effect of treatment on PFS and is powered for this endpoint. The desired operating characteristics for the PFS endpoint are used to determine the study's total sample size and overall duration. The sample size and power calculations are based on a 2-sided log-rank test for PFS and the following considerations:

- 1:1 randomization ratio between 2 treatment arms
- Target hazard ratio of 0.5 with exponential distribution for PFS. Assuming the median PFS for the control arm (rituximab+placebo) is 15 months from randomization, a target hazard ratio of 0.5 corresponds to 2-fold increase in median PFS for the treatment arm (rituximab+ibrutinib) relative to the control (ie, 30 months vs. 15 months, respectively).
- Minimum 80% power
- 2-sided overall significance level of 0.05
- One interim analysis at 70% information (50 PFS events)

The interim analysis will be based on a group sequential design with Lan-DeMets spending function with O'Brien-Fleming boundary. Using the above assumptions, and based on an accrual rate of approximately 12 subjects per month, the study will enroll approximately 150 subjects (about 75 subjects to each arm) to observe 71 events in approximately 27 months from the first subject randomized. Sample size is calculated using the software package, East 6 (Cytel Software Corp, Cambridge, MA).

Open-label Substudy Treatment Arm C

The sample size for the substudy (Arm C) is not determined according to statistical calculation as the intent of this substudy is to provide WM subjects who are considered refractory to the last prior rituximab-containing therapy access to ibrutinib as well as to evaluate safety and efficacy in the monotherapy setting. Up to 30 subjects will be enrolled in this substudy.

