10.6.2.3. Time to Next Treatment

Time-to-next treatment (TTnT) is measured from the date of randomization to the start date of any subsequent WM treatment. Subjects without subsequent treatment will be censored at the date of the last study visit. Detailed censoring rules will be included in the SAP. The analysis of TTnT will be analyzed using stratified or unstratified log-rank test as appropriate.

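### Time to next treatment: Kaplan-Meier with untreated deaths censored gives too high a proportion starting next therapy; the test and hazard ratio are unaffected

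*SAP*

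**What the plan says.** SAP section 4.1, Table 2 defines TTnT as "Time from the date of randomization to the start date of any subsequent WM treatment". Death is not part of the event. The censoring rule is "Subjects without subsequent treatment are censored at the date of the last study visit", and the analysis is "Same as PFS: stratified log-rank test, stratified Cox regression model, and Kaplan-Meier analysis".

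Protocol section 10.6.2.3 has the same rule ("Subjects without subsequent treatment will be censored at the date of the last study visit") and adds "Detailed censoring rules will be included in the SAP". The SAP adds nothing about death. The protocol synopsis, under secondary efficacy analysis, states "The distribution of OS and TTnT will be estimated using the Kaplan-Meier method similar to PFS".

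For Arm C, the text of SAP section 4.1 also plans a Kaplan-Meier estimate of TTnT, with no comparator. TTnT is second in the secondary testing order (SAP section 1.6). Neither document plans a cumulative-incidence estimate for it or a sensitivity analysis that counts death.

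**The concern.** The methods are borrowed from PFS, but the event definition is not. PFS runs to progression or "date of death due to any cause, whichever occurs first, regardless of the use of subsequent antineoplastic therapy", so under PFS nobody leaves the risk set through death without an event, and Kaplan-Meier fits. Under TTnT a subject who dies untreated is censored, and the estimator treats that subject as still able to start treatment later. One minus Kaplan-Meier then describes a setting in which nobody dies first. It is not the proportion of the randomized subjects who go on to another therapy.

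At stake is the description of a ranked secondary endpoint: the curve, its median, and any rate read from it. In Arm C there is no test or hazard ratio, so the Kaplan-Meier estimate is the only TTnT result named in SAP section 4.1.

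**Working it through.** **The plan's own figures.** The documents state no rate, median or power for TTnT, so there is no TTnT figure to reproduce. The main PFS design figure does reproduce. For a hazard ratio of 0.5, two-sided 0.05 and 80% power, Freedman's formula gives (1.960 + 0.842)² × (1.5/0.5)² = 7.85 × 9 = 70.6, hence 71 events. This point does not touch that figure.

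**Inputs for TTnT (assumptions, except the mortality scale)**
- Hazard of next treatment, *a*: 0.030 per month in Arm B and 0.012 in Arm A. Assumed.
- Hazard of death before next treatment, *d*: 0.002, 0.004 or 0.006 per month in both arms. Assumed.
- Mortality scale: Protocol section 1.1, Table 1 gives 5-year survival of 87%, 68% and 36% for 27%, 38% and 35% of patients. The mix is 0.27×0.87 + 0.38×0.68 + 0.35×0.36 = 0.619, so the all-cause hazard is −ln(0.619)/60 = 0.0080 per month. The assumed *d* is 25% to 75% of that, because some deaths follow next treatment.

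**Formulas (constant hazards)**
- Read from Kaplan-Meier: 1 − exp(−*a t*)
- Cumulative incidence: *a*/(*a*+*d*) × [1 − exp(−(*a*+*d*)*t*)]

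For example, for Arm B at 24 months with *d* = 0.006: 1 − exp(−0.72) = 51.3%, against (0.030/0.036) × [1 − exp(−0.864)] = 48.2%. The excess is 3.1 points.

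| Month | Arm | 1 − KM | Cumulative incidence, *d* = 0.002 / 0.004 / 0.006 | Excess (points) |
|---|---|---|---|---|
| 24 | B | 51.3% | 50.3 / 49.2 / 48.2% | 1.1 / 2.1 / 3.1 |
| 24 | A | 25.0% | 24.5 / 23.9 / 23.4% | 0.6 / 1.1 / 1.6 |
| 48 | B | 76.3% | 73.6 / 71.0 / 68.5% | 2.7 / 5.3 / 7.8 |
| 48 | A | 43.8% | 41.9 / 40.2 / 38.6% | 1.8 / 3.6 / 5.2 |

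**Median.** Kaplan-Meier gives ln 2/*a* = 23.1 months in Arm B. Cumulative incidence reaches one half at −ln[1 − 0.5(*a*+*d*)/*a*]/(*a*+*d*), which is 23.8 to 25.5 months over the same range of *d*.

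**Second set of assumptions.** Take the PFS design medians (15 and 30 months, Protocol section 10.5) as a stand-in for TTnT, with *d* = 0.004. At 36 months Arm B is 81.1% against 76.9% and Arm A is 56.5% against 53.1%. A simulation with 75 subjects per arm agrees (81.0 against 76.9%, and 56.4 against 53.0%). Censoring deaths at a last visit up to 12 weeks before death, instead of at death, adds only about 0.2 points.

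**Direction of the bias in the arm difference (excess in B minus excess in A)**
- Hazards 0.030 and 0.012, equal *d*, 48 months: 2.7 − 1.8 = 0.9 points (*d* = 0.002) to 7.8 − 5.2 = 2.6 points (*d* = 0.006).
- Medians 15 and 30 months, *d* = 0.004: 5.8 against 5.8 at 54 months, so about zero; 6.2 against 6.5 at 60 months, so −0.3.
- Hazards 0.030 and 0.012, with *d* = 0.002 in B and 0.004 in A, 48 months: 2.7 against 3.6, so about −0.85.

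The sign changes with the hazards and the time point.

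**The case against.** The strongest reply is that nothing inferential is at risk. The planned effect measure is the Cox hazard ratio. It and the log-rank test compare the rate of starting treatment among subjects alive and untreated, which is a legitimate cause-specific comparison. This stands.

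The size can also be questioned. TTnT is tested alongside PFS, and 71 PFS events were expected about 27 months after the first randomization. At 12 subjects per month, 150 subjects take 12.5 months, so planned follow-up then runs from about 14.5 to 27 months. The 48-month figures can apply only to long-term follow-up. At 24 months the excess is at most about 3.1% of 75, or two to three subjects, in Arm B and 1.6% of 75, or about one, in Arm A. This stands too, and the hazards are assumptions. The survival figures behind the mortality scale come from a prognostic system for newly diagnosed patients.

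A reader might infer that the curves flatter ibrutinib, because Arm B should have more next-treatment events. The documents do not support that: the sign depends on hazards they do not give, and it reverses under plausible choices. A reader might also infer that biased landmark rates are planned for TTnT. They are not; the protocol synopsis names landmark rates for OS only.

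Finally, other planned summaries help: subsequent WM agents (SAP section 3.5), and PFS and OS, which count death. None of them gives the proportion starting next therapy over time, so the point survives as one about description.

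**Conclusion.** The concern holds as a cheap improvement to how TTnT is described. Neither document names death in the TTnT rule; that untreated deaths are censored follows from the wording, which makes no exception. Given that rule, one minus Kaplan-Meier exceeds the cumulative incidence in any arm with deaths before next treatment, whatever the hazards.

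The size is not fixed by the documents. Under the first set of assumed constant hazards it is about 1 to 3 points in Arm B and 0.6 to 1.6 in Arm A at 24 months, growing with follow-up. That growth matters for the final report, because the final-CSR SAP keeps the primary SAP's methods for analyses already performed. The direction of any bias in the difference between arms is undetermined. The stratified log-rank test, the Cox hazard ratio, alpha control, the hierarchy and the 71-event PFS design are unaffected.

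**What to change.** In the TTnT row of SAP Table 2, and in the Arm C text of section 4.1:

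- Keep the stratified log-rank test and stratified Cox model for Arms A and B, and call them the cause-specific comparison.
- State that death before next treatment is a competing event.
- Present the TTnT curve, and any median or rate read from it, as cumulative incidence (Aalen-Johansen) for Arms A, B and C.
- Report the number of deaths before next treatment in each arm.

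Death dates are already collected for OS, so no new data are needed and no test changes. The cost is one estimator and a few lines of text. The one drawback is that the median may be reached less often, since cumulative incidence lies below one minus Kaplan-Meier.
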